2.4 ANALYSIS TIMING

The primary analyses will be performed after the last Confirmed Disease Progression visit occurred. The results of the statistical analyses described in this SAP will be included in a Clinical Study Report (CSR).

The data collected before CCOD (Clinical Cut-off Date) will be included in the primary analysis. The primary efficacy analysis will be performed on the Treatment period, which is defined as being from the first infusion of treatment (day1) until:

The end of the Treatment Period will be the last visit date of any efficacy measurement at week 96 (including EDSS, MRI or PRO) or withdraw date.

The duration of the treatment period is calculated as

$$\text{End of Treatment Period} - \text{first infusion date} + 1.$$

An analysis update of data collected during Safety Follow-up period will be performed once the last patient completed the safety Follow-up period. An addendum to the CSR will include results of selected statistical analyses described in this SAP, if not available at the time of the primary CSR analysis (refer to LoPo for selection of analyses). For each data type collected during the follow-up period (refer to protocol Appendix 2: Follow-up Schedule of Assessments), only listing will be provided if less than 50 patients have data available.

3. STUDY CONDUCT

3.1 RANDOMIZATION

Not Applicable

3.2 INDEPENDENT REVIEW FACILITY

Not Applicable

3.3 DATA MONITORING

Not Applicable

4. STATISTICAL METHODS

For continuous variables, descriptive statistics (e.g., number of patients [n], mean, standard deviation [SD], median, 25th and 75th percentiles, minimum, maximum) will be calculated and summarized.

For categorical variables, the number and percentage in each category will be displayed.

Statistical methods for analysis of efficacy variables are detailed in the Efficacy Analyses section below.

Unless otherwise specified, statistical tests will be two-sided and the statistical significance level will be 5%. Corresponding 95% CIs will be presented as appropriate. Although multiple statistical tests may be conducted, no adjustments to the Type 1 error rate will be made.

The analyses outlined in this SAP supersede those specified in the protocol.

4.1 ANALYSIS POPULATIONS

4.1.1 Intent-to-Treat Population

All enrolled patients who received any dose of ocrelizumab will be included in the ITT population. Patients who prematurely withdrew from the study for any reason and who did not perform any assessment for any reason will still be included in the ITT population. The ITT population will be used for all analyses except for primary analysis of NEDA and NEDA components.

4.1.2 Modified ITT population

The modified intention-to-treat (mITT) population will be defined as all patients from the ITT population excluding patients with both the screening and the baseline EDSS scores missing.

4.1.3 Per Protocol Population

The per-protocol population will consist of the subset of the ITT population defined as all patients who had 96 weeks of treatment and who did not have any major protocol violations that are deemed to potentially affect the efficacy endpoints. The analysis of the primary and secondary endpoints may be repeated if at least 10% patients are excluded from the PP population.

The following patients will also be excluded from the per-protocol population:

- Exclusions related to previous treatments
- Criteria for prior DMTs not met
- Received prohibited concomitant therapy
- Missed, not done MRIs
- MRI done after ocrelizumab infusion
- Missed post-baseline neurological assessment including EDSS

4.1.4 Pharmacokinetic-Evaluable Population

Not applicable

4.1.5 Safety Population

Safety analyses will be done on the ITT population

4.2 ANALYSIS OF STUDY CONDUCT

Patient disposition information will be summarized as follows:

- Number of patients enrolled
- Number of patients in the ITT population and PP population
- Number of patients who complete study treatment
- Number of patients who discontinue study treatment and the reasons for study treatment discontinuation
- Number of patients who discontinue study and the reasons for study discontinuation
- Number of patients entering the safety follow-up
- Number of patients who roll over to the long term extension of Ocrelizumab study
- Number of patients who received any DMT (Disease modifying treatment) after Ocrelizumab discontinuation

Major protocol violations, including violations of inclusion/exclusion criteria collected during the study via PDMS will be summarized and listed.

4.3 DEMOGRAPHIC AND BASELINE CHARACTERISTICS

The following demographic and baseline characteristics will be summarized for the ITT population:

- Age (years) as continuous variable and age in the following categories:
 - $\leq 40, > 40$
 - $\leq 18, 18 < - \leq 40, > 40$
- Gender
- Self-reported race and ethnicity
- Female reproductive status
- Country
- Height (cm), weight (kg), and Body Mass Index (BMI: kg/m²)
- Smoking history (never, current, previous); if previous, years since last use and years relative to MS diagnosis; if current or previous, years of smoking.
- Qualifying events for enrollments
 - 1) Only enrolled due MS Relapse
 - 2) Only enrolled due to MRI Activity
 - Only T1 Gd-enhanced lesion
 - Only New or enlarging T2 lesion
 - Both
 - 3) Enrolled due to MS relapse and any MRI activity

Disease activity before enrollment will be summarized as:

- 1) the number of relapse over the year prior to inclusion ($\leq 1, >1$) having the date of the last relapse
 - within 6 months: before enrollment
 - within 6 months and 12 months before enrollment
- 2) EDSS at baseline ($<2.5, \geq 2.5$)
- 3) MRI at Week 8: Number of T2 lesions and presence of T1 Gd+ (Yes/No)

These variables will be summarized for the following groups of patients:

- number of prior DMTs (1,2)
- last DMT prior to study enrolment

Prior DMT Use

- Number of prior DMTs (1, 2)
- Number of patients by last DMT* prior to study enrolment
- Reason for discontinuing the last DMT
- Duration of last DMT and its category (≤ 6 months, >6 and ≤ 12 months, > 12 months), overall and by DMT type
- Time from last DMT to first Ocrelizumab infusion, overall and by DMT type

For patients with 2 previous DMT, the following will also be presented

- Number of patients by first DMT
- Duration of first DMT and its category, overall and by DMT type
- Reason for discontinuation for each previous DMT

*for DMT type, the eCRF terms "Interferon β 1a", "Interferon β 1b" and "Peg Interferon β 1a" will be grouped into "Interferon".

Multiple Sclerosis History

- Duration since MS Symptom Onset and its category (≤ 3 years, >3 and ≤ 5 years, >5 years and ≤ 10 years, >10 years)
- $(\text{date of baseline visit} - \text{onset date of MS symptoms} + 1) / 365.25$
- Duration since RMS Diagnosis and its category (≤ 2 years, >2 and ≤ 5 years, >5 years and ≤ 10 years, > 10 years)
- $(\text{date of baseline visit} - \text{date of diagnosis of RRMS} + 1) / 365.25$
- Baseline EDSS and its category (<2.5 and ≥ 2.5)

Screening Disease History– Relapse

- Number of relapses in the last year as continuous and in categories (0, 1, 2, 3, ≥ 4) and (≤ 1 and >1)
- Duration since last onset of MS relapse prior to enrollment and its category (≤ 3 months, >3 and ≤ 6 months, >6 months)
 $(\text{date of baseline visit} - \text{date of last onset of MS relapse prior to enrollment} + 1) / 30.4375$
- Sites and symptoms for the most recent relapse

Note that for this analysis, if the date of the relapse is completely missing or if only the year is available, this will not be included in the analysis. If the day is missing, it will be imputed to the first day of the month.

Screening Disease History - MRI

- Number of Gd-enhancing T1 lesions at Screening as continuous and in categories (0,1,2,3, ≥ 4) at Screening
- Number of T2 lesions at Screening

Week 8 MRI – Baseline reset MRI

- Number of Gd-enhancing T1 lesions at Baseline reset as continuous and in categories (0,1,2,3, ≥ 4)

Ocrelizumab—F. Hoffmann-La Roche Ltd

15/Statistical Analysis Plan MA30005

- Volume of T2 lesions at Baseline reset
- Normalized brain volume at Baseline reset

4.4 EFFICACY ANALYSIS

4.4.1 Primary Efficacy Endpoint

Protocol-defined event definition

The definition of a protocol-defined event of disease activity is the occurrence of at least one of the following individual events while on treatment with ocrelizumab:

- A protocol-defined relapse defined as an occurrence of new or worsening neurological symptoms attributable to MS. Symptoms must persist for > 24 hours and should not be attributable to confounding clinical factors (e.g., fever, infection, injury, adverse reactions to medications), and immediately be preceded by neurological stability for at least 30 days.
- 24-weeks CDP based on increase in EDSS while on treatment with ocrelizumab
- A new T1 Gd-enhanced lesion on MRI after week 8
- A new and/or enlarging T2 hyperintense lesion on MRI after week 8

The MRI activity will be calculated on the events starting from week 8 (baseline reset).

Patient without any of this protocol-defined event of disease activity will be considered as NEDA = Yes (no evidence of disease activity).

The primary endpoint, NEDA, as well as the related disease activities components and combinations listed below, will be evaluated on the mITT population based on the following analysis principles:

- Patients, who discontinued treatment prior week 96 due to death or lack of efficacy, will be considered as having evidence of disease activity at the time of treatment discontinuation (e.g NEDA="NO", Relapse="Yes" and CDP="Yes").
- Patients who discontinued treatment for reasons other than death or lack of efficacy with no evidence of disease activity at the time of early treatment discontinuation will be excluded from the analysis as their disease activity status cannot be ascertained.

This is further summarized in the table below:

Endpoint	Patients who discontinued treatment without related disease activities prior week 96 due to:	
	death or lack of efficacy	Other reason than death or lack of efficacy with no evidence of disease activity
NEDA	included with evidence of disease activity (NEDA=NO)	excluded
Relapse	included with evidence of disease activity (Relapse=Yes)	excluded

24-weeks CDP	included with evidence of disease activity (CDP="Yes")	
 • If discontinuation before confirmation, excluded • If discontinuation after confirmation, included when CDP="Yes"
T1 Gd-enhanced lesions after week 8	included with evidence of disease activity	excluded
New/enlarging T2 lesions after week 8	included with evidence of disease activity	excluded

Analysis of binary NEDA

The proportions of patients with:

- NEDA
- Treatment discontinuation due to lack of efficacy or death without events prior the withdrawal
- Relapses
- No Relapse
- 24-weeks CDP
- No 24 weeks CDP
- T1 Gd-enhanced lesions after week 8
- No T1 Gd-enhanced lesions after week 8
- New/enlarging T2 lesions after week 8
- No New/enlarging T2 lesions after week 8
- MRI activity (T1 Gd-enhanced lesions or new/enlarging T2 lesions)
- No MRI activity
- Relapses or MRI activity
- 24-weeks CDP or MRI activity
- Clinical activity (Relapses or 24-weeks CDP)
- No clinical activity
- Relapses and MRI activity
- 24-weeks CDP and MRI activity
- Relapses and 24-weeks CDP

post-baseline up to the Week 96 visit will be calculated and presented with a two-sided 95% Clopper-Pearson exact confidence interval.

Protocol-Defined Relapse definition

A protocol-defined MS relapse is an occurrence of new or worsening neurological symptoms attributable to MS that meets the following criteria:

- Symptoms must persist for >24 hours and should not be attributable to confounding clinical factors (e.g., fever, infection, injury, adverse reactions to medications)
- Symptoms should be preceded by neurological stability for at least 30 days
- Symptoms should be accompanied by new objective neurological worsening determined with a timely EDSS/ Functional Systems Score (FSS) assessment, consistent with an increase of at least:
 - ≥ 0.5 points on EDSS scale
 - or ≥ 2 points on one of the following FSS scales: pyramidal, ambulation, cerebellar, brainstem, sensory, or visual
 - or ≥ 1 point on two or more of the following FSS scales: pyramidal, ambulation, cerebellar, brainstem, sensory, or visual

Information related to a PDR will be captured on a clinical relapse event case report form (CRF) page (Multiple Sclerosis Relapse). If the following criteria are satisfied, the clinical relapse will qualify as a PDR:

1. Clinical relapse is reported on eCRF.
2. Check-box of “Did symptoms persist for >24 hours and were not being attributable...” on the Clinical MS relapse event is checked.
3. Check if the first EDSS assessment at a visit (unscheduled or scheduled) on or after the onset date of the relapse is increased by ≥ 0.5 steps from the previous EDSS; or selected FSS domains relevant to the relapse event (pyramidal, ambulation, cerebellar, brainstem, sensory, or converted visual) are increased by ≥ 2 points on one domain or ≥ 1 point on two or more domains. When deriving this step do the following:
 - Take the last EDSS/FSS score before each clinical relapse onset date
 - Take the first EDSS/FSS score on or after each clinical relapse onset date
 - Calculate the difference between the two scores
 - Select clinical relapses where there is an increase of ≥ 0.5 in EDSS or ≥ 2 on one appropriate FSS domain or ≥ 1 on two or more appropriate FSS domains
4. For each relapse that satisfies the 3 criteria above, check if the following relapses are within 30 days (i.e., the onset dates are ≤ 30 days apart). If they are within 30 days, then the later relapses are not PDR.

24-Week Confirmed Disability Progression (CDP) definition

Disability Progression as measured by EDSS is defined a ≥ 1 -point increase in EDSS score from a baseline EDSS score of 0.0–5.5 inclusive, and a 0.5-increase from a baseline EDSS score higher than 5.5. Because of the variability of EDSS, a single measurement at the baseline visit might not provide a sufficiently reliable baseline EDSS. Therefore, using an average score from two separate measurements may improve the reliability of baseline EDSS and the reliability of confirmed disability progression seen in the study. In the analysis of CDP, baseline EDSS is defined as the average of the EDSS scores at the screening and baseline visits (of note, any baseline visits occurring after the first dosing date will be disregarded in the computation of the baseline EDSS score), without rounding. If one of the EDSS scores from the screening or baseline visit was missing, the other was used for baseline EDSS.

Initial progression can happen at any scheduled or unscheduled visit during the 96-week treatment period.

An initial disability progression becomes confirmed if the following conditions are met:

1. A sustained change in EDSS for a minimum of 24 weeks (-2 weeks) from the initial progression event i.e. the change in EDSS must be sustained at all available (scheduled or unscheduled) visits for a minimum of 24 weeks ($\geq 168-14$ days= 154 days) after initial progression. An “Early Discontinuation” visit can be used as a confirmation visit if it falls into the visit window (defined in the protocol) of any scheduled visit. The EDSS assessments (if any) between the initial disability progression and the confirmation of disability progression should be at least as high as the minimum change required for progression.
2. Scheduled visits within 30 days after the onset of a clinical relapse that meets conditions 1, 2 and 3 of a protocol-defined relapse definition cannot be used for confirmation of disability progression. The confirmation of the disability progression must then be based on the EDSS assessment at the next scheduled visit (which is not within 30 days of a protocol defined relapse).
3. If a patient has a missing assessment at the scheduled visit taking place at 24 weeks (≥ 154 days) after an initial progression, the confirmation of the disability progression must be based on the assessment at the next scheduled visit.

For the patients who have the initial progression at week 96 and roll over to the long term extension of Ocrelizumab study, a confirmation EDSS assessment will be collected in the long term extension (Liberto) study.

Patients who complete the treatment period without confirmed progression of disease will be censored at the date of their last EDSS assessment during the treatment period. Patients with an initial assessment of disease progression who subsequently discontinue

from the study without further assessments will not be considered to have confirmed disease progression, if the discontinuation reason is not lack of efficacy or death. Patients who discontinue from the study due to lack of efficacy or death without confirmed progression of disease will be imputed as having an event (i.e., CDP) at the time of discontinuation.

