4.4.2 Secondary Efficacy Endpoints

For all continuous secondary efficacy endpoints, in addition to the model based analyses, they will also be summarized descriptively at each assessment visit. Analysis populations are specified for each endpoint.

4.4.2.1 Proportions of NEDA patients during the initial 24-week and the initial 48-week period

This endpoint will be analyzed on the mITT population using the same approaches as described above in Section 4.4.1, for the proportion of NEDA patients assessed during the initial 24-week period and during the initial 48-week period.

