4.4.2.8 Time to onset of first new and/or enlarging T2 lesion

This endpoint will not be analyzed as the measurement of T2 lesion by MRI is only performed at week 24, 48 and 96, while the actual onset time can be very different from the MRI visit.

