4.4.2.9 Time to onset of first T1 Gd-enhanced lesion

This endpoint will not be analyzed as the measurement of T1 lesion by MRI is only performed at week 24, 48 and 96, while the actual onset time can be very different from the MRI visit.

4.4.2.10 Total number of T1 Gd-enhanced lesions detected by brain MRI at Weeks 24, 48 and 96

The analyses will include patients in the ITT population. Data from unscheduled assessments will not be included in this summary or analysis.

The following analyses will be presented:

- Number and percentage of patients having 0, 1, 2, 3, and greater than 1 and greater than 3 lesions at weeks 24, 48 and 96.
- Number and percentage of patients having 0, 1, 2, 3, and greater than 1 and greater than 3 lesions in total detected at week 24, 48 and 96.
- The unadjusted and adjusted rates of lesion occurrence at weeks 24, 48 and 96 and the unadjusted and adjusted rate combining week 24, 48, 96 will be calculated:
 - The unadjusted rate will be the ratio of the total number of T1 Gd-enhanced lesions divided by the total number of interpretable MRI scans at each visit.
 - The adjusted rate will be derived using a negative binomial model. The dependent variable in the model will be the total number of T1-Gd-enhanced lesions. The model will be adjusted for the following covariates:
 - disease duration
 - presence of T1 Gd-enhanced lesions at screening (Yes/No),
 - presence of relapses prior screening as per CRF (Yes/No)
 - number of previous DMTs (1, >1).

In order to account for patients potentially receiving varying numbers of brain MRI scans during the study, the log-transformed number of brain MRI scans received will be included in the model as an “offset”.

- For the analysis above using negative binomial model for adjusted rate, if the model doesn't converge due to a high number of zero T1 Gd-enhanced lesion counts, other models, such as logistic regression model will be considered based on the same baseline variables. Patients having zero T1 Gd-enhanced lesions (but not missing) up to withdrawal will be considered as not having an event.

- Histogram of the count (0, 1, 2, 3, >1, >3) of T1 Gd-enhanced lesions at Weeks 24, 48 and 96, and during all visits (Weeks 24, 48 and 96) combined will be produced.

A descriptive analysis on the number of T1 Gd-enhanced lesions at screening and week 8 will also be performed.

4.4.2.11 Change in total T2 lesion volume detected by brain MRI from Week 8 to Week 96

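### SAP 4.4.1 sets no minimum MRI data for NEDA=Yes in treatment completers; read literally, an event-free completer with no evaluable scan after Week 8 is a success, and sensitivity analyses A to E do not test this

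*SAP*

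**What the plan says.** SAP 4.4.1 lists four events: protocol-defined relapse, 24-week confirmed disability progression (CDP), a T1 Gd-enhanced lesion after Week 8, and a new or enlarging T2 lesion after Week 8. It then states: "Patient without any of this protocol-defined event of disease activity will be considered as NEDA = Yes (no evidence of disease activity". NEDA and its components "will be evaluated on the mITT population based on the following analysis principles". Those principles deal only with patients who stopped treatment before Week 96. Stopping for death or lack of efficacy counts as disease activity. Patients who stopped for another reason without activity "will be excluded from the analysis as their disease activity status cannot be ascertained".

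The mITT population (SAP 4.1.2) is the ITT population "excluding patients with both the screening and the baseline EDSS scores missing". It has no MRI condition.

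The same section reports "No MRI activity" and the other MRI components under the same principles. SAP 4.4.2.1 carries the rule to the earlier windows, "using the same approaches as described above in Section 4.4.1, for the proportion of NEDA patients assessed during the initial 24-week period" and likewise for 48 weeks. On timing, SAP 4.4.2.8 says that "the measurement of T2 lesion by MRI is only performed at week 24, 48 and 96". SAP 4.7 says that missing values are not imputed unless a section specifies otherwise. Protocol 6.7 leaves missing-data handling to the SAP.

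**The concern.** Two of the four NEDA components can be seen only on a scan. If a completer has no evaluable scan after Week 8, those two components are unknown, yet following the written rule produces a success. An event-free discontinuer is set aside because the status is unknown, although a completer without scans is just as unknown on MRI. For such completers the error can go only one way, upward.

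The affected outputs are the primary proportion, the proportion without MRI activity, and 24- and 48-week NEDA. Numbers of interpretable scans per visit could be derived from SAP 4.4.2.10, but no planned output links missing scans to NEDA status. A reader of the report could not tell how many successes rest on absent scans.

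**Working it through.** **1. Planned precision (SAP 2.3).** Clopper-Pearson, n = 750. For 225/750 (30%) the 95% CI is 26.74% to 33.42%, half-width 3.34. For 375/750 (50%) it is 46.36% to 53.64%, half-width 3.64. Both agree with the stated 3.3 and 3.6. At 60% the half-width is 3.57.

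**2. Does any planned analysis reach these patients?**
- A: as its text explains, removes patients who discontinued treatment. Completers are untouched.
- B: moves the MRI baseline to screening.
- C: replaces protocol-defined relapse with any clinical relapse.
- D: counts relapses only from Week 8.
- E: imputes a Gd lesion where a scan exists, was done after infusion and shows none. An absent scan is not covered.
- Per-protocol repeat (SAP 4.1.3): drops patients with missed MRIs, but it is optional, depends on at least 10% of patients being excluded, and drops patients for other reasons too.

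**3. Size.** The documents give no missing-MRI rate, so every input here is an assumption:
- m = share of analysed patients with no evaluable MRI after Week 8: 1% (about 8 of 750) or 5% (about 38)
- C = probability of no clinical event = 0.75
- N = true NEDA = 0.30, 0.50 or 0.60
- scans are missing independently of disease status

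Formulas:
- Literal rule: (1−m)N + mC, so bias = m(C−N)
- Exclude only event-free patients without MRI: (1−m)N / (1−mC)
- Count them as NEDA=No: (1−m)N, so bias = −mN
- Exclude every patient without MRI, whatever the clinical events: (1−m)N / (1−m) = N, so bias = 0

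| Bias, percentage points | N = 30% | N = 50% | N = 60% |
|---|---|---|---|
| Literal, m = 1% | 0.01 × 0.45 = +0.45 | 0.01 × 0.25 = +0.25 | 0.01 × 0.15 = +0.15 |
| Literal, m = 5% | +2.25 | +1.25 | +0.75 |
| Exclude event-free only, m = 5% | 0.285/0.9625 = 29.61%: −0.39 | 0.475/0.9625 = 49.35%: −0.65 | 0.570/0.9625 = 59.22%: −0.78 |
| Count as No, m = 5% | −1.50 | −2.50 | −3.00 |

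**4. 24-week NEDA.** Only the Week 24 scan falls in the window, so m is the share missing that one scan. If 5% miss it and 5% to 25% of patients would fail on MRI only, the bias is 0.05 × 0.05 = +0.25 to 0.05 × 0.25 = +1.25 points.

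**5. What bounds the answer.** Take m = 5% and 30% NEDA among scanned patients. Coding the unscanned event-free patients all No gives 0.95 × 0.30 = 28.5%. Coding them all Yes gives 28.5 + 0.05 × 75 = 32.25%. If all of them would have failed on MRI, the truth is 28.5%, yet excluding only them gives 29.6%. That exclusion is therefore not a bound.

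**The case against.** The best reply is that the literal reading is not the intended one. Scoring an absent scan as no lesion is in effect an imputation, and SAP 4.7 rules out imputation unless it is specified. SAP 4.4.2.10 separates zero from missing in its fallback model: "Patients having zero T1 Gd-enhanced lesions (but not missing) up to withdrawal will be considered as not having an event". The exclusion of event-free discontinuers shows the same caution. A reader might infer that the sponsor plans to count missing scans as successes; the documents do not support that. What stands is narrower: neither SAP 4.7 nor 4.4.2.10 assigns a NEDA status to a completer without scans or removes that patient from the mITT denominator, while 4.4.1 does state a rule, and that rule returns Yes.

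The second reply is rarity, and for 96 weeks it largely stands. Patients unable to complete an MRI are excluded at entry, Protocol 4.5.7 asks for all efforts to scan before infusions, and all three later scans must be missing. It does not answer the 24-week endpoint, where one missed scan suffices.

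Third, requiring only one later scan is itself a choice: a completer with a clean Week 24 scan and nothing afterwards remains NEDA=Yes. This is fair, and it is why the fix asks for a count of incomplete MRI.

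Two related matters do not carry the point. Protocol 4.6.2 plans visits without MRI during pregnancy and breastfeeding, but lists this under treatment discontinuation and would rarely remove every scan from Week 24 to Week 96. How T2 is scored when the Week 8 scan is missing is a separate question, and may be settled in the MRI technical manual, which is not among the documents.

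**Conclusion.** The point holds as a gap in a stated rule. It is a minor-to-moderate correction to a reported estimate. The study is single-arm and descriptive, so no test decision depends on it.

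The direction is certain for the patients affected; the size is not known. Under the assumptions above, the upward bias in 96-week NEDA is 0.15 to 0.45 points at 1% missing and 0.75 to 2.25 points at 5%, below the planned half-widths in each case.

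A reader might infer that the headline rate is materially inflated, for instance because 38 event-free patients without scans would give 33.6% under the literal rule against 30.1% if excluded and 28.5% if counted as No. The documents do not support that. They give no frequency of missing scans, and the gaps of 3.5 and 5.1 points are differences between coding rules, neither comparator being the true rate.

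**What to change.** In SAP 4.4.1, state that NEDA=Yes and "No MRI activity" require at least one evaluable MRI after Week 8 within the analysis window; for 24-week NEDA this is the Week 24 scan. Treat event-free completers without one as not ascertainable, as is done for event-free discontinuers. Completers who miss only some later scans stay in the 96-week analysis.

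Report how many event-free completers have no MRI, and how many have incomplete MRI, after Week 8.

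Add three sensitivity rows:
- not-ascertainable completers all counted as NEDA=Yes;
- the same patients all counted as NEDA=No; these two rows are the bounds;
- every completer with no MRI after Week 8 excluded, whatever the clinical events, which is unbiased if scans are missing completely at random.

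Do not describe exclusion of event-free patients only as a bound: under random missingness it is biased slightly downward, and it can lie above the truth if missingness is informative.

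As clarifications only, say how the T2 component is scored when the Week 8 scan is missing but later scans exist, and whether a patient with interrupted treatment and MRI-free visits is analysed as a discontinuer or a completer.

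The cost is a few sentences, one count and three table rows, with no new data. The downside is slightly fewer evaluable patients and a slightly less favourable estimate.
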